4.4.1.1 Ocular and multimodal imaging assessments

Best-corrected visual acuity (BCVA)

BCVA score is based on the ETDRS VA chart assessed at a starting distance of 4 meters. The BCVA score (actual value and change from Baseline) will be summarized over time.

A listing of BCVA score over time will be presented.

Change from Baseline in BCVA score over time will be analyzed using a longitudinal mixed effects model repeated measures (MMRM). The model's fixed effects will include visit along with the following covariates:

- Baseline BCVA score
- Age (continuous)
- Region (U.S/Canada and the rest of the world (ROW))

Visit will be treated as a repeated variable within a patient. Patient and visit will be treated as factor variables. An unstructured variance-covariance structure will be applied to model the within-patient errors. If there are convergence issues with the model, then an AR (1) covariance structure may be fitted. The model will be fitted using the Restricted Maximum Likelihood method (REML). Denominator degrees of freedom will be estimated using Satterthwaite's approximation.

Graphical presentation for least square means and 95% confidence intervals will be used to illustrate trends over time.

Diabetic Retinopathy Severity Score (DRSS)

The ETDRS DRSS score (actual value and change from baseline) assessed from Ultrawidefield Fundus Photography (UWF-C) and from Color Fundus Photography (FP-7M) will be summarized over time presenting the following proportion of patients along with a twosided 95% Clopper-Pearson exact confidence interval:

- Number and percentage of patients with >=2 step ETDRS DRSS improvement from baseline
- Number and percentage of patients with >=3 step ETDRS DRSS improvement from baseline

These proportions will be described graphically (bar chart) to illustrate trends over time

Intraretinal fluid (IRF) and Subretinal fluid (SRF)

The IRF/SRF assessed from Spectral Domain-Optical Coherence Tomography (SD-OCT) will be described as below:

Proportion of patients along with a two-sided 95% Clopper-Pearson exact confidence interval:

 Number and percentage of patients with Absence and Presence of intraretinal fluid over time:

- Absence of IRF is defined as IRF-Cystoid Spaces equals to Absent, or Definite outside center subfield only.
- Presence of IRF is defined as IRF-Cystoid Spaces equals to Questionable, or Definite only noncystoid center subfield involved, or Definite cystoid center subfield involved.

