- Number of patients with recurrence of IRF over time (i.e. Number of patients with recurrence of IRF over time are defined as patients with presence of IRF at any of the post baseline timepoints (week 4, week 8, week 12, week 16, week 20 and week 24) regardless of their baseline status..)
- Number and percentage of patients with Absence and Presence of subretinal fluid over time:
 - Absence of SRF is defined as SRF equals to Absent or Definite outside center subfield only.
 - Presence of SRF is defined as SRF equals to Questionable or Definite center subfield involved.
- Number of patients with recurrence of SRF over time (i.e., Number of patients with recurrence of SRF over time are defined as patients with presence of SRF at any of the post baseline timepoints (week 4, week 8, week 12, week 16, week 20 and week 24) regardless of their baseline status.)

Additionally, the time to IRF resolution will be defined as the number of days from Baseline to first absence of IRF. The Kaplan-Meier method will be used to estimate the survival function for the time to first IRF resolution. Kaplan-Meier rates and Greenwood 95% CI using log-log transformation will be presented at week 4, week 8, week 12, week 16, week 20 and week 24. Kaplan-Meier plots (presented as cumulative incidence) will be produced. Patients without IRF resolution, discontinued from treatment, will be censored at the last IRF assessment. The patients with absence of IRF at baseline are not considered at risk, therefore, they will be excluded from the analysis.

The same analysis will be produced for the time to SRF resolution.

Retinal thickness using Spectral Domain-Optical Coherence Tomography (SD-OCT)

The measurement of Central subfield thickness (CST ILM-RPE) (actual value and change from Baseline) will be summarized over time up to week 20 and Safety Follow-up period

week 24). In addition, the change from baseline in CST will be analyzed using a longitudinal MMRM. The model's fixed effects will include visit along with the baseline CST ILM-RPE value, age and region covariates.

The same analyses will be performed on Center Point Thickness (CPT ILM-RPE) and on macular volume (Center SubField Volume ILM-RPE, the center subfield (CSF) is the circular region centered on the anatomic fovea with a radius of 500 microns).

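### The SAP counts any post-baseline fluid as 'recurrence' of IRF or SRF, without requiring that fluid was seen before or had cleared

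*SAP*

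**What the plan says.** In SAP 4.4.1.1, the part on intraretinal fluid (IRF) and subretinal fluid (SRF) lists by-visit presence and absence, then a count of patients with recurrence, for each type of fluid.

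- IRF: "Number of patients with recurrence of IRF over time are defined as patients with presence of IRF at any of the post baseline timepoints" (Weeks 4, 8, 12, 16, 20 and 24), "regardless of their baseline status".
- SRF, in the same terms: "Number of patients with recurrence of SRF over time are defined as patients with presence of SRF at any of the post baseline timepoints", again ignoring baseline status.
- Presence is read from a single visit, and a doubtful grade counts. For IRF, "Presence of IRF is defined as IRF-Cystoid Spaces equals to Questionable" or either of two definite grades involving the center subfield. For SRF, "Presence of SRF is defined as SRF equals to Questionable or Definite center subfield involved".

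The time-to-resolution analysis that follows defines resolution as the first absence of fluid and does use history. Its censoring rule reads "Patients without IRF resolution, discontinued from treatment, will be censored at the last IRF assessment", and its risk set is restricted: "The patients with absence of IRF at baseline are not considered at risk, therefore, they will be excluded from the analysis". The same analysis is planned for SRF.

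The line introducing the list asks for proportions with exact 95% intervals. The presence/absence rows say number and percentage; the recurrence rows say number only and name no denominator. SAP 2.2.1 does not list recurrence as an endpoint; it lists changes from baseline in IRF and SRF.

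**The concern.** Recurrence means that something was there, went away and came back. The SAP rule tests only whether fluid was seen at least once after baseline. Three kinds of eye therefore enter the count without any fluid having come back:

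- eyes wet at baseline that never dry;
- eyes wet at baseline and at one or more early visits that then dry for good;
- eyes dry at baseline in which fluid appears once, for the first time.

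The first group is unresolved in the time-to-resolution analysis and 'recurrent' in the row just above it. The third is outside the risk set of one analysis and an event in the other. Nothing elsewhere in the SAP or protocol narrows the rule. For comparison only, protocol 5.3.5.3 uses the word for adverse events in the ordinary sense: an event that resolves and later comes back.

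A study report table headed recurrence would be read as fluid returning despite treatment. Most of what it showed could be slow or incomplete clearing, which means something different clinically.

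**Working it through.** The SAP gives no recurrence figure, so there is none to reproduce. The check is logical first and illustrative second.

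**1. Which visit patterns count?** Baseline plus six post-baseline visits, each wet or dry, give 2^7 = 128 complete patterns.

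| Baseline | Patterns | SAP rule | Presence-absence-presence | Counted with no return |
|---|---|---|---|---|
| Wet | 64 | 63 | 57 | 6 |
| Dry | 64 | 63 | 42 | 21 |
| All | 128 | 126 | 99 | 27 |

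Only two patterns escape the SAP rule: never wet, and wet at baseline only. The 6 are one unbroken wet run from baseline lasting through 1 to 6 post-baseline visits (the last being never resolved). The 21 are a single run of fluid within six visits, 6 × 7 / 2 = 21. The SAP rule misses no true recurrence; it only over-counts. These are counts of possible patterns, not patient frequencies.

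**2. A case that needs no relapse model.** Suppose every eye is wet at baseline, a share h is dry by Week 4 and fluid never returns. The row reports 1 − h: 90%, 80%, 70% or 50% for h = 0.1, 0.2, 0.3 or 0.5. True recurrence is 0%.

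**3. Illustration with relapse.** All rates are assumed: b = share wet at baseline, r = resolution per visit, q = relapse per visit, taken equal to new onset. Visits are complete, and each visit depends only on the one before.

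Share counted by the SAP rule = 1 − b·r·(1−q)^5 − (1−b)·(1−q)^6.

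IRF with b = 0.90, r = 0.25:
- q = 0.05: 1 − 0.225 × 0.7738 − 0.10 × 0.7351 = 75.2%
- q = 0.15: 1 − 0.225 × 0.4437 − 0.10 × 0.3771 = 86.2%
- q = 0: 0.90 × 0.75 = 67.5%

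Return after observed resolution in eyes wet at baseline = b·Σ r(1−r)^(k−1)·[1 − (1−q)^(6−k)], with first dry visit k = 1 to 5. At q = 0.05 this is 0.90 × 0.1256 = 11.3%. Full enumeration, adding the small part from eyes dry at baseline (0.1-0.7%), gives 11.4% at q = 0.05 and 29.9% at q = 0.15.

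| Case | SAP rule | Fluid returning after resolution |
|---|---|---|
| IRF, b 90%, r 25%, q 5-15% | 75-86% | 11-30% |
| IRF, b 90%, r 50%, q 5-15% | 58-76% | 17-43% |
| SRF, b 15-40%, r 25-50%, q 5-15% | 32-73% | 3-26% |

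With no return at all and r = 50%, the IRF row still shows 0.90 × 0.50 = 45%. In the SRF case, first onset with no later return is 15-47% of patients.

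COVID-19 censoring (SAP 4.4) and missed visits are not modelled.

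**The case against.** The strongest reply is that the SAP hides nothing. The rule is written out, ignoring baseline status is an explicit choice, and anyone holding the SAP can reproduce the count. The study is exploratory, the rows are descriptive and recurrence is not a listed endpoint. On that view this is a wording point. The limit on impact is right. But being explicit makes the rule reproducible, not the label accurate, and a study report table will be read by its label.

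Second, SAP 4.4 places all exploratory outcomes in the mITT population, so a default denominator can be inferred. That is fair for a count of any presence. It is not a suitable base for recurrence, because eyes that never cleared cannot have a return.

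Third, the contrast with time to resolution should not be pressed too far. The censoring sentence also mentions stopping treatment, and that analysis has to exclude eyes dry at baseline for its own reasons. The contrast shows that the SAP recognises unresolved eyes; it does not prescribe the risk set for a separate count. The finding rests on the recurrence definition itself.

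Fourth, the sizes are assumed, and the no-return figure simply restates the assumed Week 4 resolution. Faster IRF resolution narrows the gap, as the 50% row shows, but does not close it.

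Last, a sequence rule has its own weakness. Since doubtful grades count as presence, an assumed false doubtful grade at 2%, 5% or 10% of dry visits would alone produce 6.9%, 16.2% or 29.7% apparent recurrence among resolved eyes (IRF, r = 25%, no true return). This is a reason to keep that definition optional and report the doubtful grades, not to keep the present label.

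**Conclusion.** The concern holds for both IRF and SRF. Followed exactly, the SAP reports persistent, slowly clearing and first-onset fluid as recurrence. This is a definition that is wrong as written, not a missing detail.

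That conclusion rests on the text alone. The size rests on assumed rates, but in every case tried the SAP count is well above the share of patients whose fluid came back. The consequence is two mislabelled descriptive rows. It does not reach the listed endpoints, the by-visit tables or the Kaplan-Meier analyses. It should be fixed, because the fix is trivial and the label would mislead.

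**What to change.** **Minimum.** Rename the rows as any post-baseline presence of IRF and of SRF, and state the denominator, including how patients with no graded post-baseline SD-OCT are handled. Renaming costs nothing.

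**If recurrence is to be reported:**
- Define it as presence (at baseline or later), then absence at a graded visit, then presence at a later graded visit.
- Use as denominator the eyes with an observed resolution and at least one later graded visit.
- Count a missed or ungradable visit as neither state.
- Show eyes dry at baseline separately, and give never-resolved and first-onset-only eyes their own rows.
- Report how many returns rest only on doubtful grades.

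This needs SAP wording and minor programming on grades already collected; no new data.

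The price is a smaller denominator and wider intervals. Assuming 99 treated patients (the enrolment figure in SAP 2.3), complete visits and exact 95% intervals:
- IRF (b 90%, r 25%): 11/69 = 16% (8-27%) at q = 5%, to 30/70 = 43% (31-55%) at q = 15%.
- SRF (b 25%, r 35%): 5/31 = 16% (5-34%) to 17/45 = 38% (24-53%).

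In the IRF case only about 1-2 eyes dry at baseline would be in the denominator, so that row would be a count only.

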4.2 METHOD OF TREATMENT ASSIGNMENT

This is an exploratory, non-randomized, open-label study. After initial written informed consent has been obtained, all patients will receive a unique screening number assigned through an IxRS. After all the screening procedures and assessments have been completed, and eligibility has been established for a patient, the study site will obtain the patient's identification number through IxRS.

Patients who do not meet the criteria for participation in this study (screen failures) may qualify for 1 re-screening opportunity (for a total of 2 screenings per patient; see Section 3.1.1.2 for further details).

No more than 50% of patients enrolled will have mild or moderate PDR (defined as ETDRS DRSS 60 through 65C [lp et al. 2012]).

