2.2 OUTCOME MEASURES

2.2.1 Exploratory Endpoints

To explore the associations over time between clinical assessments, multimodal imaging assessments, AH biomarker patterns and genetic polymorphisms:

- Proportion of patients with a ≥2-step ETDRS DRSS improvement from baseline over time
- Proportion of patients with a ≥3-step ETDRS DRSS improvement from baseline over time
- Changes from baseline in BCVA (as measured on the ETDRS chart) over time
- Changes from baseline in IRF (intraretinal fluid) over time
- Changes from baseline in SRF (subretinal fluid) over time
- Changes from baseline in CST over time
- · Changes from baseline in multimodal imaging over time including:
 - Central retinal thickness
 - Foveal avascular zone (FAZ) / retinal nonperfusion
 - Vessel density
 - Periphery status (ischemia and proliferation)
 - Microaneurysm location, number, and turnover
 - Ischemic area
- Changes from baseline in AH biomarker patterns over time including:
 - Proteins, including but not limited to: cytokines, chemokines, and growth-, angiogenesis-, and complement-related factors, etc.
 - Metabolites, including but not limited to: lipids, sugars, amino acids, etc.
- Genetic polymorphisms via standard clinical genotyping
- Advanced analytics tools (e.g., artificial intelligence-based tools) for the assessment of clinically relevant features

2.2.2 Pharmacokinetic Endpoints

Not Applicable.

2.2.3 Safety Endpoints

The Safety endpoints are:

- Incidence and severity of adverse events
- Description of ocular assessments
- Study treatment exposure and Anti-VEGF exposure for fellow eye
- Laboratory assessments (only HbA1c assessments)
- Concomitant medication
- Concurrent ocular procedures

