Additionally, the time to first absence of DME will be analyzed. The first absence of DME is defined as the number of days from baseline to first time reaching CST (ILM-RPE) < 305 um. The Kaplan-Meier method will be used to estimate the survival function for the time to first absence of DME. Kaplan-Meier rates and Greenwood 95% CI using log-log transformation will be presented at week 4, week 8, week 12, week 16, week 20 and week 24. Kaplan-Meier plots (presented as cumulative incidence) will be produced.

Patients without absence of DME discontinued from treatment, will be censored at the last CST assessment.

Outcome measures using Ultra-widefield Fluorescein Angiography (UWF-FA)

The UWF-FA imaging type was scheduled at screening post-eligibility visit and week 20. The screening visit will be considered as Baseline visit.

The baseline actual value and change from baseline to week 20 will be summarized for the following endpoints:

- Total area of capillary Non-perfusion within the macula ETDRS grid
- Distance of the capillary Non-perfusion to the Center of Fovea
- Perimeter length of total capillary Non-perfusion
- Total area of capillary Non-perfusion within the eye
- Total area of assessable retina for capillary Non-perfusion
- Total area of visible retina
- Total area of fluorescein leakage within the ETDRS grid
- Distance of the fluorescein leakage to the Center of the Fovea
- Perimeter length of total fluorescein leakage

Total area of leakage within the eye

The following proportion of patients along with a two-sided 95% Clopper-Pearson exact confidence interval will be summarized at Baseline and week 20:

- Number and percentage of patients with absence of macular ischemic non perfusion (capillary loss):
 - Absence defined as total area of capillary non perfusion within the macula of 0 to 0.10 mm²
- Number and percentage of patients with absence of ischemic non perfusion within the Total Retinal Area:
 - Absence defined as total area of Capillary non perfusion within the eye of 0 to 1 mm2
- Number and percentage of patients with absence of Macular leakage:
 - Absence is defined as total area of fluorescein leakage within the macula of 0 mm2

The number of patients and percentage at baseline and week 20 visit will be described for the following endpoints:

- Change in fluorescein leakage within ETDRS grid from Screening Visit
- Absence of New Vessels on Disc (NVD)
- Absence of New Vessels Elsewhere (NVE) within 7 field grid

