- Absence of New Vessels Elsewhere (NVE) beyond 7 field grid

Adaptive optics

For Adaptive optics assessments, the number of patients who underwent these assessments at baseline and week 20 visit will be summarized.

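### New vessels on angiography are tabulated at baseline and at Week 20 without linking the visits by eye, so the tables show neither clearance nor new onset

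*SAP*

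**What the plan says.** SAP 2.2.1 lists "Periphery status (ischemia and proliferation") among the changes from baseline in multimodal imaging. SAP 4.4.1.1 treats the screening ultra-widefield angiogram as baseline and compares it with Week 20, using three kinds of summary:

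- **Continuous measures** (areas, distances and perimeters of non-perfusion and leakage): baseline value and change from baseline to Week 20. This is a within-eye change.
- **Three binary rows**, namely absence of macular non-perfusion (0 to 0.10 mm²), of non-perfusion in the total retinal area (0 to 1 mm²) and of macular leakage (0 mm²): a proportion at each visit, where the Clopper-Pearson "exact confidence interval will be summarized at Baseline and week 20".
- **A last list**, introduced by "The number of patients and percentage at baseline and week 20 visit will be described for the following endpoints". It holds "Change in fluorescein leakage within ETDRS grid from Screening Visit", then "Absence of New Vessels on Disc (NVD)", NVE within the 7-field grid, and "Absence of New Vessels Elsewhere (NVE) beyond 7 field grid". No interval is planned for this list.

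SAP 4.7 does not impute missing data outside the repeated-measures models. SAP 4.4.2 plans no sensitivity analyses.

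**The concern.** The endpoint is a change in the same eye, but for NVD and NVE the planned result is two separate snapshots. An eye that never had new vessels counts as absent at both visits. An eye that lost them and an eye that gained them cancel out. The reader sees a net shift at most, and cannot see how many affected eyes cleared or how many unaffected eyes developed new vessels.

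The snapshots may also cover different eyes. The SAP defines no set of eyes gradable at both visits, so a difference between the percentages may reflect which eyes lack a Week 20 angiogram.

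The three binary non-perfusion and leakage rows have the same gap, but it costs less there because the continuous measures are analysed as within-eye change.

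**Working it through.** The plan states no figure for these endpoints, so there is none to reproduce. The documents give no baseline rate of NVD or NVE. All counts below except the total of 99 are assumptions chosen to show the mechanism.

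**Inputs.** N = 99 (SAP 2.3, the increased sample size). Assumed: lesion absent in 79 eyes at baseline and 89 at Week 20, so 99 − 79 = 20 eyes are affected at baseline.

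**Step 1: what two snapshots show.** Absence is 79/99 = 79.8% and 89/99 = 89.9%. Where the SAP plans Clopper-Pearson intervals (the non-perfusion and leakage rows), these counts would give 70.5 to 87.2 and 82.2 to 95.0. For NVD and NVE only the counts and percentages would appear.

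**Step 2: what they leave open.** Let b be the eyes that clear and c the eyes with new onset. The snapshots fix only b − c = 89 − 79 = 10. With d = (b − c)/N, the paired Wald interval is d ± 1.96 × √[(b + c) − (b − c)²/N]/N. The exact McNemar p-value tests b out of b + c against one half. Clearance is b/20 and new onset is c/79, each with a Clopper-Pearson interval.

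| b, c | Cleared (95% CI) | New onset (95% CI) | Net change, points (paired 95% CI) | McNemar p |
|---|---|---|---|---|
| 10, 0 | 10/20 = 50% (27.2 to 72.8) | 0/79 = 0% (0 to 4.6) | 10.1 (4.2 to 16.0) | 0.002 |
| 15, 5 | 15/20 = 75% (50.9 to 91.3) | 5/79 = 6.3% (2.1 to 14.2) | 10.1 (1.5 to 18.7) | 0.041 |
| 20, 10 | 20/20 = 100% (83.2 to 100) | 10/79 = 12.7% (6.2 to 22.0) | 10.1 (−0.6 to 20.8) | 0.099 |

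First row: √(10 − 100/99)/99 = 0.0303, and 10.1 ± 1.96 × 3.03 gives 4.2 to 16.0. Treating the visits as independent gives 0.2 to 20.0 in every row. The planned table would be identical for all three rows.

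**Step 3: missing angiograms.** Suppose no eye changes, but 10 of the 20 affected eyes have no gradable Week 20 angiogram. If percentages are taken over eyes assessed, absence goes from 79/99 = 79.8% to 79/(99 − 10) = 79/89 = 88.8%. That is an apparent rise of 9.0 points, close to the 10.1 points in Step 2. The angiography paragraph does not state the denominator, so this too is an assumption.

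**The case against.** The strongest reply is that the SAP handles most of its binary imaging endpoints better than this, and that the study is single-arm and exploratory. Much of that stands, and it rules out several stronger readings.

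- **A reader might infer that no binary imaging endpoint is paired by eye.** Intraretinal fluid is tabulated by visit ("Number and percentage of patients with Absence and Presence of intraretinal fluid over time"), but SAP 4.4.1.1 also plans Kaplan-Meier time to first resolution with fluid-free eyes at baseline excluded, and the same for subretinal fluid. The fluid endpoints are therefore outside this point.
- **A reader might infer that change from baseline is not estimated.** For non-perfusion and leakage it is, on the continuous scale, and the last list itself contains a leakage-change item. For NVD and NVE, the difference between the percentages gives the net change if the same eyes are seen twice. What is missing is the transitions and a paired interval.
- **A reader might infer that never-affected eyes dominate the percentages.** That depends on a prevalence the documents do not give. Protocol 4.2 says "No more than 50% of patients enrolled will have mild or moderate PDR", which is an upper limit on DRSS 60 through 65C and not a rate of NVD or NVE. If half of affected eyes clear and none are new, never-affected eyes make up from 94.7% down to 9.6% of eyes absent at Week 20 as assumed baseline prevalence runs from about 10% to 95%.
- **A reader might infer that overlapping intervals would hide a change in NVE.** The SAP plans no interval for NVE; the Clopper-Pearson sentence governs the preceding list.

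DRSS improvement of at least 2 or 3 steps is a within-eye measure and may partly capture regression. It is a composite severity grade and does not report clearance or onset of NVD or NVE. SAP 4.4 defers association analyses to a separate document, but does not say that it covers lesion transitions.

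**Conclusion.** The point holds for NVD and both NVE endpoints, whose only planned result is two unlinked percentages without an interval. It holds in weaker form for the three binary non-perfusion and leakage rows, where a within-eye continuous analysis exists alongside.

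Under the assumed counts, one planned table is compatible with clearance anywhere from 50% to 100% of affected eyes and with 0 to 10 new cases. Missing data alone could produce an apparent 9-point change. These figures show what the tables cannot distinguish; they do not predict this trial's results. The conclusion itself rests only on the SAP text and on the fact that two marginal percentages do not determine the paired table. In an exploratory study this is a reporting gap that should be closed. It does not threaten the study's main objective.

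**What to change.** In SAP 4.4.1.1, for NVD, NVE within the 7-field grid, NVE beyond it, and the three binary non-perfusion and leakage rows, add the following among eyes gradable at both visits:

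1. a baseline-by-Week-20 2×2 shift table, with the number of eyes not gradable at one or both visits;
2. the proportion cleared among eyes with the lesion at baseline and the proportion with new onset among eyes without it, each with a Clopper-Pearson 95% interval;
3. the paired difference in proportions with a paired 95% interval.

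The planned percentages can stay, with their denominators stated. The cost is one extra descriptive table per endpoint from data already collected. Clearance will rest on a small denominator, so its interval may be wide: 27 to 73% for 10 of 20 in the illustration.
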